## **Randomization**

Once a participant has completed the Screening/Consent Visit and is found to be eligible to participate, they will be assigned a sequential study number which will be used to identify data. They will be scheduled for a Baseline/Randomization Visit prior to the start of study intervention. The study statistician, who is responsible for making and maintaining the study randomization schedule, will provide the project manager with the randomization assignment for each participant. Each participant's assignment will be revealed to both study staff and participant at the completion of the Baseline/Randomization Visit. The participant will be given specific information regarding their treatment assignment and confirm availability for the upcoming sessions.

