### **Participant Selection**

#### **Inclusion Criteria**

- 1) Women Veterans who experienced military sexual trauma;
- 2) Meets DSM-V criteria for PTSD due to military sexual trauma
- 3) Difficulty falling asleep or difficulty staying asleep (insomnia)
- 4) Ability to give informed consent;
- 5) Willing to participate in either TC-TSY or CPT;
- 6) Available to attend the study intervention at the scheduled times.

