## **Methods**

### ***Data Collection (See Table 1: Study Flowchart and Data Collection Schedule)***

Participants will be assessed at five time-points during the study. Following the phone pre-screening interview, the participant will be scheduled for the Screening/Consent Visit (Time 0) for further determination of eligibility. If eligible, participants will be scheduled for the Baseline/Randomization Visit (Time 1) followed by the Mid-Treatment Visit (Time 2), the 2-Week Post Treatment Visit (Time 3) and the 3-Month Follow-Up Visit (Time 4). Each study visit will last 2-3 hours and includes collection of self-report measures, interview-based assessments, psychophysiological assessment, and immunological measures. Finally, if the participant completes intervention and elects to participate in the crossover intervention, they will be asked to complete several self-report measures (PCL, BDI, BPI, PSQI, VR-12 & Treatment Evaluation Form) before treatment, midway through treatment and again 2-weeks and 3-months post treatment. Participants opting to do the crossover intervention will not be compensated and will be given the option to complete the measures via phone.

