## **PTSD Severity:**

- The Clinician Administered PTSD Scale (CAPS-5) is the gold-standard for assessing PTSD. The CAPS uses a clinician-administered diagnostic instrument that assesses lifetime and current PTSD diagnosis and symptoms and global PTSD symptom severity. The CAPS also yields a continuous measure of the severity of both overall PTSD and of the four PTSD symptom clusters. It assesses the validity of the participant's responses and has excellent psychometric properties. The Past-Month version will be administered at Baseline and the Past Week version will be administered at each of the follow-up visits. CAPS-5 interviews will be audio-recorded for quality assurance purposes.
- The PTSD Checklist (PCL-5) is a 20-item self-report rating-scale instrument that parallels diagnostic criteria for PTSD, as delineated in the Diagnostic and Statistical Manual of Mental Disorders (DSM-V). The PCL is the standard measure of PTSD symptoms in the VA and can be used to determine PTSD diagnosis and PTSD symptom severity.

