**Table 1: Study Flowchart and Data Collection Schedule**

	Pre-Screen Phase	Screening Visit a	Baseline/ Randomization Visit	Mid-Tx Visit	2-Week Post Treatment Visit	3-Month Follow-Up Visit	Crossover Intervention d or subsequent survey
		Time-0	Time-1	Time-2	Time-3	Time-4	
Phone Screening	X						
Chart Review/Med. Clearance	X	X					
Inclusion/Exclusion Review	X	X					
Informed Consent/HIPAA		X					
AEs/Con Meds/VA Groups Log		X	X	X	X	X	
Basic Demographics/Updates		X	X	X	X	X	X
DRRI-2 Combat Experiences		X					
Childhood Trauma Ques.		X					
Life Events Checklist		X					
MINI (for DSM-5)		X					
Berlin Questionnaire		X				X	
Epworth Sleepiness Scale		X				X	
RANDOMIZATION			X b				

Beck Depression Inventory			X	X	X	X	X
Difficulties in Emotion Regulation Scale			X	X	X	X	
Dissociative Experiences Scale			X	X	X	X	
Brief Pain Inventory			X	X	X	X	X
Pittsburgh Sleep Quality Index		X	X	X	X	X	X
Patient Health Questionnaire			X	X	X	X	
PROMIS Measures			X	X	X	X	
PROMIS Social Isolation							X
CAPS-5			X	X	X	X	
PTSD (PCL-5)							X
Chronic Pain Survey (BPI)							X
PTSD-Checklist-5		X	X	X	X	X	X
Intervention Tracking				X	X	X	X
VR-12			X	X	X	X	X
12-Lead ECG			X		X		
Dark-Enhanced Startle Session e			X		X	X	
Heart Rate Variability Measure			X		X	X	
Blood Draw/Processing			X		X	X	
Provide Compensation		X	X	X	X	X	
Offer alternate intervention							X
Polysomnogram (optional)		X c,e					

aGiven the nature of this study, the T-0 and T1 Visits may be combined into one visit

bRandomization will occur after all other Baseline/Randomization Visit procedures have been completed

cThe sub-study will be described at the screening visit and if interested, consent will be obtained for eligible participants. The PSG can be completed at any time during study participation

dIf the participant elects to do the crossover intervention, measures will be administered by phone or in-person at baseline, mid-treatment and at 2-weeks and 3-months post treatment

e Given the availability of equipment, this measure will only be conducted for participants in Atlanta

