## Statistical Analysis Post hoc: Equivalence Testing

### Detailed Methods:

While the original RCT was designed for inequality hypothesis testing, given the lack of differences seen between the 2 treatments (both performed well), we additionally conducted equivalence tests of means between the two treatment groups using two one-sided unequal-variance t-tests (TOST). These equivalence tests were performed using the TOSTER v.0.4.0 package for R [REFS Lakens (2017); Lakens, Scheel and Isager (2018)]. The changes from baseline to each follow-up time point were computed for each participant. These change scores were then used to perform two one-sided t-tests (TOST) between the two treatment groups to test for equivalence and reject the presence of the smallest effect size of interest (SESOI). This approach essentially checks to see if the 90% confidence interval bounds for the mean difference between the two groups are within the limits defined by the SESOI. Similar to Sloan, et.al. (2022), a margin of 10 was used as the SESOI. Sloan was only interested in one-side of the margin and performed non-inferiority tests since they assumed one treatment might be inferior to the other. However, we did not have an initial assumption that one treatment would be better than the other, so two one-sided tests or TOSTs were performed to test for equivalence within +/- 10 points. This SESOI was used for both the CAPS-5 and PCL-5 change score differences between the two treatment groups. It has also been suggested that a difference as small as 5 points for the CAPS-5 may be useful for comparing treatments for PTSD so the mean and standard deviation of all changes scores are also reported by group and time for descriptive comparisons. For clinical diagnostic comparisons, similar to Schnurr, et.al. (2022), the percentage of participants at each time point who still have PTSD are reported as well as the percentage who achieved a clinical response (reduction of CAPS-5 severity scores by 10 or more points from baseline), loss of diagnosis (CAPS-5 change  $\leq -10$ , no PTSD diagnosis and CAPS-5 severity score  $< 25$ ), as well as those who achieved remission (loss of diagnosis plus CAPS-5 score  $< 12$ ). All statistical analyses completed using SPSS version 27.0.0.0 [IBM Corp (2020)] and R version 4.1.2 [R Core Team (2021)].

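### The baseline CAPS-5 is not used to confirm the PTSD entry criterion, and the post hoc diagnosis percentages do not require a CAPS-5 diagnosis at baseline

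*Combined protocol and SAP*

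**What the plan says.** All references are to the combined protocol and SAP.

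- **Entry criterion.** Inclusion criterion 2 reads "Meets DSM-V criteria for PTSD due to military sexual trauma". It names no instrument, no threshold and no rule for the index event.
- **When eligibility is decided.** Under Data Collection, after the phone pre-screen "the participant will be scheduled for the Screening/Consent Visit (Time 0) for further determination of eligibility", and only women found eligible go on to the baseline visit. The Randomization section has the same order: "Once a participant has completed the Screening/Consent Visit and is found to be eligible to participate", she receives a study number and a baseline appointment. In Table 1 the row "Inclusion/Exclusion Review" is marked at Pre-Screen and Time 0 only.
- **Instruments.** Table 1 marks the MINI and the PCL-5 at Time 0. The CAPS-5, which the PTSD Severity section treats as the reference measure, is marked from Time 1 to Time 4: "The Past-Month version will be administered at Baseline and the Past Week version will be administered at each of the follow-up visits".
- **Order at Time 1.** Footnote b of Table 1 states: "Randomization will occur after all other Baseline/Randomization Visit procedures have been completed". Footnote a allows Time 0 and Time 1 to be a single visit.
- **Outcome.** The post hoc section (Detailed Methods) says that "the percentage of participants at each time point who still have PTSD are reported". It adds clinical response (a CAPS-5 fall of at least 10 points), loss of diagnosis (that fall, no PTSD diagnosis, and a score under 25) and remission (loss of diagnosis with a score under 12). None of these is limited to women who had a CAPS-5 diagnosis at baseline.

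**The concern.** Entry and outcome rest on different instruments, and no rule connects them. A woman judged to have PTSD at Time 0 may not meet CAPS-5 criteria at Time 1, or her CAPS-5 diagnosis may be anchored to an event other than military sexual trauma. The plan does not say what happens then, although the interview is already done when the assignment is given.

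At stake are the absolute percentages a clinical reader will take from the report: how many women still have PTSD after each treatment, how many lost the diagnosis and how many remitted. The words still and loss imply a diagnosis at the start, which the definitions do not require. How well the stated population, PTSD due to military sexual trauma, is documented on the trial's own reference instrument is also left open.

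**Working it through.** **Figures in the plan.** The documents give no number or share of randomised women without CAPS-5 PTSD at baseline, so there is no figure to reproduce on this point. The Power Analysis section gives 104 completers (52 per group), used here only to convert shares into counts.

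**Step 1: is there a rule?** Data Collection, Randomization and the Inclusion/Exclusion Review row all place the decision at Time 0 or before. The CAPS-5 row starts at Time 1. Footnote b puts the CAPS-5 ahead of assignment, so the result is available in time. No section provides for a second eligibility review or for withholding assignment on that result. A CAPS-5 non-case can therefore be randomised.

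**Step 2: what each outcome rule does with a baseline non-case** (taking the severity score as unable to fall below zero).

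- Persisting PTSD: if she is still negative at follow-up, she counts as a woman without PTSD, with no treatment effect needed.
- Entry score of 10 or more: take entry at 20 and follow-up at 10. Change = 10 - 20 = -10, no diagnosis, and 10 is below 25, so she is scored as having lost a diagnosis. Since 10 is also below 12, she is scored as remitted.
- Entry score below 10: the largest possible fall is under 10 points. She can meet none of response, loss of diagnosis or remission, and only enlarges the denominator.

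**Step 3: illustration for persisting PTSD.** Let q be the share of non-cases, p the true persistence among baseline cases, and r the share of non-cases who have PTSD at follow-up.

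Reported persistence = (1 - q) × p + q × r.

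Assume p = 60% and r = 0. Neither these values nor q comes from the documents.

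| q | Non-cases among 104 | Reported persistence |
|---|---|---|
| 5% | 104 × 0.05 = 5.2 | 0.95 × 60% = 57% |
| 10% | 104 × 0.10 = 10.4 | 0.90 × 60% = 54% |
| 20% | 104 × 0.20 = 20.8 | 0.80 × 60% = 48% |

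Taking r = 0 gives the largest reduction. The shift is q × (p - r), which disappears if r equals p. If q and r are the same in both arms, the between-arm difference in this percentage is multiplied by (1 - q).

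**Step 4: direction for loss of diagnosis.** Let L be the true rate among baseline cases and a the share of non-cases who meet the rule.

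Reported rate = (1 - q) × L + q × a.

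Take L = 40% (also an assumption) and q = 20%. If a = 0, the rate is 0.80 × 40% = 32%. If a = 1, it is 32% + 20% = 52%. The error can go either way, depending on where non-cases score at entry.

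**The case against.** The strongest reply is that criterion 2 still binds. It demands DSM PTSD due to military sexual trauma, the CAPS-5 is completed before assignment, Time 0 and Time 1 may be one visit, and no section tells a site to disregard a CAPS-5 showing that the criterion is not met. The Time 0 wording triggers a study number and an appointment; it does not forbid later exclusion. This stands against the inference that a site following the plan would randomise such women. The documents support only that it can.

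A second reply is that PTSD is screened at entry. The MINI is a DSM-based interview, and the protocol says the PCL-5 can be used to determine the diagnosis. Entering women on one diagnostic instrument and measuring outcome on another is a legitimate design. That is fair: the gap is possible disagreement between instruments and an unstated index event, not an absence of screening. Likewise, the combat and childhood trauma questionnaires record exposure. They do not show that women with PTSD from those causes were admitted.

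Third, a reader might infer that dilution undermines the equivalence claim. The documents do not support this. The two one-sided tests are run on mean CAPS-5 and PCL-5 change scores, whereas the diagnosis-based percentages are reported for clinical description, with no equivalence test described for them.

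Finally, a percentage given at each time point may include baseline, in which case the share without CAPS-5 PTSD would be visible. This is possible, but the section does not say so, and it would not change the denominators used at follow-up.

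**Conclusion.** The point holds as a cheap improvement. The written procedure settles eligibility before the CAPS-5 and provides no rule for using its result, and the post hoc diagnosis outcomes do not require a diagnosis at baseline. The documents do not show that any woman without baseline CAPS-5 PTSD was enrolled.

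The size is unknown. The fall from 60% to between 57% and 48% rests on three assumptions: a non-case share of 5% to 20%, true persistence of 60%, and every non-case staying negative. Persisting PTSD can be understated, while loss of diagnosis and remission can be off in either direction. Randomisation should make the non-case share similar in the two arms, so the main harm is to the absolute percentages and to any between-arm difference in them. No effect on the mean-change equivalence test is shown.

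**What to change.** (a) Report, by arm, how many women met CAPS-5 PTSD at baseline. Calculate persisting PTSD, loss of diagnosis and remission among those women, with the figures for all randomised participants beside them. Baseline status is measured before assignment, so this subset keeps the randomised comparison, and the data are already collected. The cost is a slightly smaller denominator: at the illustrative shares, about 104 - 5 = 99 down to 104 - 21 = 83 completers.

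(b) Only if enrolment is still open, add an eligibility review to Table 1 at Time 1, after the CAPS-5 and before the assignment is given, and state which instrument and which index event establish criterion 2. No new procedure is needed; the cost is a few late screen failures. The post hoc section describes results already obtained, so (b) may come too late to matter, and (a) is then the request that remains.

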## **Study Intervention**

### **Trauma Center-Trauma Sensitive Yoga**

The yoga intervention consists of a standardized trauma-sensitive Hatha yoga protocol developed by Emerson, Spinazzola and colleagues for use with civilian women with treatment-resistant PTSD. Hatha yoga is a general term to describe the practice of physical postures, breath work, and mindfulness—what is commonly referred to in the West simply as “yoga.” There are many styles of Hatha yoga (e.g., Iyengar, vinyasa, Ashtanga, Bikram), but when the term Hatha yoga is used in the West in contrast to another specified style, it most often designates a more gentle, slower-paced approach to the physical postures. Our protocol uses this gentler, slower approach. It involves ten weekly 90-minute group sessions of Trauma Center-Trauma Sensitive Yoga. Sessions address themes related to establishing safety, individual choice, being in the present moment, and taking effective action. The intervention will be conducted by yoga teachers certified in Trauma Center-Trauma Sensitive Yoga. Study staff will provide participants in the yoga intervention with detailed information related to the sessions. In addition, instructional DVDs will be provided to participants in the yoga intervention to facilitate practice at home. For participants who do not have access to a DVD player, a link will be provided which will direct participants to the private online videos on YouTube. These videos are hidden from the public, therefore the only way to gain access is by entering the link provided by the study team. Finally, reminder calls will be made each week to ensure optimal group attendance. During follow-up visits, study staff will assess whether participant engaged in at-home TC-TSY practice, and the frequency of at-home practice (via use of DVD/online videos, breathing techniques etc.) using an intervention tracking form.

### **Cognitive Processing Therapy-Cognitive**

The control group, Cognitive Processing Therapy (CPT), is one of the gold-standard therapies for PTSD treatment in the VA mental health system. CPT is a cognitively-based, trauma focused treatment which will be led by two licensed clinical social workers who work in the Women's Trauma Program. As per the treatment protocol, there are twelve 90-minute weekly sessions. The group sessions focus on identifying how thoughts change as a result of trauma exposure and ways in which to realistically evaluate these maladaptive thoughts and come up with more accurate alternative thoughts. Also per protocol, group members do not share their specific trauma details in group. These sessions will be conducted concurrently with the yoga intervention throughout the course of the study. Study staff will provide participants in the CPT group with detailed information related to the sessions. Reminder calls will be made each week to ensure optimal group attendance. During follow-up visits, study staff will assess the degree to which participant engaged in homework assignments and used strategies learned in group using an intervention tracking form.

### **Compensation (Atlanta)**

Participant compensation will be provided following each study visit and following each treatment session. Participants will receive \$40 for completion of the Screening/Consent, Baseline/Randomization and Midpoint Visits. For completion of the 2-Week and 3-Month post-treatment visits, participants will receive \$60. For each treatment session, participants will receive \$15. Compensation will be sent in the form of a VA check or via direct deposit. Each method of payment will be discussed and participants will indicate their preference at the initial visit. Eligible participants who consent and complete the sub-study will receive \$60 once they have completed the sleep study. The total possible compensation for completion of the study is \$480. In certain cases, if the participant has to return a second time to complete a study visit, they may receive additional

compensation of up to \$20. For visits when the participant receives the heart-rate variability monitor, compensation will be sent as soon as the device is returned to the study site. Participants taking part in the crossover intervention will not receive compensation for completion of the study forms.

### **Compensation (Portland)**

Participant compensation will be provided following each study visit and following each treatment session. Participants will receive \$40 for completion of the Screening/Consent, \$60 for Mid-treatment and 3-Month Follow-up visit, and \$85 for the Enrollment/Baseline/Randomization and 2-Week Post-Treatment Visits. For each treatment session, participants will receive \$10 for which they attend. Compensation will be sent in the form of a VA check or via direct deposit. Each method of payment will be discussed, and participants will indicate their preference at the initial visit. The total possible compensation for completion of the study is \$430-450. In certain cases, if the participant has to return a second time to complete a study visit, they may receive additional compensation of up to \$20. For visits when the participant receives the heart-rate variability monitor, compensation will be sent as soon as the device is returned to the study site.

Participants taking part in the crossover intervention will not receive any compensation.

## **C. POTENTIAL RISKS/DISCOMFORTS TO STUDY PARTICIPANTS AND MEASURES TO PREVENT OCCURRENCE**

### **Self-Report and Interview-Based Assessments**

The assessments include questions about exposure to stressors and other topics that might produce transitory distress in some individuals. There is the potential for participants to experience embarrassment or other negative consequences if some of the experiences were disclosed, particularly if their identity was linked to interview data. We think that these risks are minimal given the protections in place to maintain confidentiality and the plans to respond to participants who experience distress.

### **Study Interventions**

***Trauma Center-Trauma Sensitive Yoga:*** There are physical risks in participating in the yoga intervention, as well as the potential for emotional distress during yoga sessions. The protocol has been designed specifically for women with PTSD. It is expected that some women will experience intense emotion during the yoga. The protocol has been designed to mitigate these risks and address physical and emotional distress if necessary.

***Cognitive Processing Therapy-Cognitive:*** There is a risk for transitory psychological distress in participating in the control condition, cognitive processing psychotherapy. This intervention is evidence-based and manualized and some psychological distress is expected. Clinicians providing this intervention are highly trained to respond to any such distress.

### **Venipuncture**

The blood draw may cause mild discomfort, bruising, redness, or swelling. Study staff will discuss the process of having blood drawn with the participant to determine if there are any concerns or past difficulties with having blood drawn. Pertinent information will be relayed to the phlebotomist beforehand. These procedures are only done by skilled personnel in order to reduce the risk of any negative reactions. The risks associated with the blood draw are unlikely and, if they occur, should resolve within a few days.

